8.7.B. If yes, please describe A) the type of data to be transferred, B) who the data will be transferred to, C) where the data will be transferred, and D) how the data will be sent.	The stool samples will be send to the University of Ottawa for sequencing for bacterial composition analysis. The samples will be send, labelled with a study identifier to our collaborator in the [name] lab. The data for further analysis will be send back electronically and encrypted to the BCCHR researchers to store on password-protected computers.								
8.8. Data Transfer to Institution 8.8.A Will the researchers be receiving data from other sites?:	no								
8.8.B If yes, please describe A) the type of data to be received, B) who the data will be received from, C) where it will be received from, and D) how the data will be received.									
8.9. Data Linkage 8.9.A. Will the data be linked to any other data source (including a biorepository)?	no								
8.9.B. A) Identify the data set, B) how the linkage will occur, and C) explain how confidentiality regarding the shared information will be preserved.									
9. Documentation - Clinical Study [View Form]									
9.1.A. Protocol Examples of types of protocols are listed on the right. Click Add to enter the required information and attach the documents.	
  
 Document Name	Version	Date	Password (if applicable)	
   
 Ethics proposal	5	January 23, 2018	[View]	
  
	Document Name	Version	Date	Password (if applicable)	Ethics proposal	5	January 23, 2018	[View]
Document Name	Version	Date	Password (if applicable)						
Ethics proposal	5	January 23, 2018	[View]						
9.1.B. Health Canada regulatory approval (receipt will be acknowledged)	Document Name Version Date Password (if applicable)								
9.1.C. FDA IND or IDE letters (receipt will be acknowledged)	Document Name Version Date Password (if applicable)								
9.2. Consent Forms Examples of types of consent forms are listed on the right. Click Add to enter the required information and attach the forms.	
  
 Document Name	Version	Date	Password (if applicable)	
   
 Consent Form UVB study	5.2	February 13, 2018	[View]	
  
	Document Name	Version	Date	Password (if applicable)	Consent Form UVB study	5.2	February 13, 2018	[View]
Document Name	Version	Date	Password (if applicable)						
Consent Form UVB study	5.2	February 13, 2018	[View]						
9.3. Assent Forms Examples of types of assent forms are listed	Document Name Version Date Password (if applicable)								

on the right. Click Add to enter the required information and attach the forms.
													

9.4. Investigator Brochures/Product Monographs Please click Add to enter the required information and attach the documents.
	
Document Name Version Date Password (if applicable)
												

9.5. Advertisement to Recruit Participants Examples are listed on the right. Click Add to enter the required information and attach the documents.
	
  
 Document Name	Version Date	Password (if applicable)	
   
 Recruitment Poster UVB study	5 January 23, 2018	[View]	
 
 facebook page UVB study	1 May 15, 2017	[View]	
  
	Document Name	Version Date	Password (if applicable)	Recruitment Poster UVB study	5 January 23, 2018	[View]	facebook page UVB study	1 May 15, 2017	[View]			
Document Name	Version Date	Password (if applicable)											
Recruitment Poster UVB study	5 January 23, 2018	[View]											
facebook page UVB study	1 May 15, 2017	[View]											

9.6. Questionnaire, Questionnaire Cover Letter, Tests, Interview Scripts, etc. Please attach each separately. Please click Add to enter the required information and attach the documents.
	
Document Name Version Date Password (if applicable)
												

9.7. Letter of Initial Contact Please click Add to enter the required information and attach the forms.
	
  
 Document Name	Version Date	Password (if applicable)	
   
 Letter of initial contact research participant	3 May 4, 2017	[View]	
  
	Document Name	Version Date	Password (if applicable)	Letter of initial contact research participant	3 May 4, 2017	[View]						
Document Name	Version Date	Password (if applicable)											
Letter of initial contact research participant	3 May 4, 2017	[View]											

9.8. Data collection forms and Other Documents 9.8.A. Please attach Data collection Forms, Chart extraction forms, CRF or other documents. Examples of other types of documents are listed on the right.
	
  
 Document Name	Version Date	Password (if applicable)	
   
 Response to REB review	3 May 12, 2017	[View]	
 
 Fitzpartick scale	3 May 4, 2017	[View]	
 
 UVBstudy peer review	1 February 1, 2017	[View]	
  
	Document Name	Version Date	Password (if applicable)	Response to REB review	3 May 12, 2017	[View]	Fitzpartick scale	3 May 4, 2017	[View]	UVBstudy peer review	1 February 1, 2017	[View]
Document Name	Version Date	Password (if applicable)											
Response to REB review	3 May 12, 2017	[View]											
Fitzpartick scale	3 May 4, 2017	[View]											
UVBstudy peer review	1 February 1, 2017	[View]											

9.8.B. If a Web site is part of this study, enter the URL below. Since URL's may change over time or become non-existent, you must also attach a copy of the documentation contained on the web site to this section or provide an explanation.
													

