	
microbiota composition. Also serum vitamin D (25-hydroxy vitamin D) will be measured before and after the UVB exposure as a marker of previous UVB exposure before the experiment.
 
Subjects will be healthy Caucasian females between 19-40 years of age with a Fitzpatrick skin type I, II or III to minimise the variability in skin responses towards the UVB-NB light since fair skin colour is less adapted to absorb the UVB radiation than dark coloured skin.
 
The microbiota composition will be analysed with 16S rRNA Illumina sequencing and calculated for differential abundance on phylum level.
 
Statistical analysis: The statistical analysis will focus the personal microbiota composition variation after NB-UVB light exposure in comparison to before the UVB light exposure. Because we collect two samples before and two samples after the UVB exposures, each individual can serve as her own internal control.

5.2. Inclusion Criteria Inclusion Criteria. Describe the participants being selected for this study, and list the criteria for their inclusion. For research involving human pluripotent stem cells, provide a detailed description of the stem cells being used in the research.
	
Healthy Caucasian females between 19-40 years of age. Fitzpatrick skin type I, II or III (see box 9.8A for Fitzpatrick skin type assessment).

5.3. Exclusion Criteria Exclusion Criteria. Describe which potential participants will be excluded from participation, and list the criteria for their exclusion.
	
The participants will be excluded if they have skin photo sensitivity or taking medication that promotes photo sensitivity of their skin. Also participants that have been on vacation to a sunny destination since October 2017 or visit tanning beds on a regular basis will be excluded because they have been exposed to UVB radiation.

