
5.4. Recruitment Provide a detailed description of the method of recruitment. Include where applicable A) Who will contact prospective participants B) by what means this will be done. C) How prospective participants will be identified D) Ensure that any letters of initial contact or other recruitment materials are attached to this submission on Page 9.
	
The recruitment will be done via social media with Facebook (UVBstudy page). The recruitment advertisement is included in the submission. The researcher will contact prospective participants after they voluntarily contacted the study email address: [contact] Initial contact will be through email conversation until the potential participant expresses interest participating by email. Once the participant has signed the consent form, a study identifier will be assigned to the participant to protect the individuals identity.

5.5. Recruitment of Normal/Control Participants Describe how prospective normal/control participants will
	
Each participant will serve as her own control. All participants will be recruited the same way.

be identified, contacted, and recruited, if the method differs from the above.
	

5.6. Use of Records If existing records (e.g. health records, clinical lists or other records/databases) will be used to IDENTIFY potential participants or COLLECT DATA, please describe how permission to access this information, and to collect and use this information will be obtained.
	
No existing records will be used for this study.

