
5.7. Summary of Study Procedures
	
Participants will contact the study coordinator and will be invited to participate by and email that will be sent along with the consent form. A first meeting will be set up between the research coordinator and the participant at the Skin Care Center to explain the protocol and to sign consent forms. Also four stool collection kits will be handed to the participant. After signing the consent form, the Fitzpatrick skin type will be assessed with the hand of a questionnaire about the sun exposure habits.
 
The participant is responsible to collect two stool samples during the week prior to the first light exposure and store it in her freezer at home.
 
On the Monday of the first NB-UVB exposure, the research coordinator will confirm that a stool sample is collected by the participant. The participant will be referred to the lab at Life Labs to collect one blood sample (one tube of 15 ml, approximately one table spoon full) and will later go to The Skin Care Centre at VGH where the participants will be assessed under supervision of dr. [name] MD, for their first full body NB-UVB exposure. The participants will wear specialised goggles to protect the eyes from the UVB rays, and wear broad spectrum sunscreen on face and hands to protect these areas from the light. The NB-UVB light exposure will happen in a full body cabin, like an upright tanning bed, and will take no longer than 5 minutes. A time will be scheduled for the next two sessions with the participants. On Wednesday and Friday, the participant will receive a NB-UVB dose that is 10% higher than the first visit, if tolerated well.
 
Description of blood collection procedure at Life Labs: A blood sample will be taken by first applying a tourniquet to the upper arm. The skin on the inner side of the elbow will be sterilised and a small, sterile needle will be inserted into the vein. Two blood collection tubes will then be attached to the needle which will fill with blood. When the tube is full, the needle will be removed. A plaster or small bandage will be applied to cover the site where the needle

was removed.

Blood samples will be marked with their study identifiers and analysed in Life labs for of serum 25-hydroxy vitamin D3 according to Standards Council of Canada’s Good Laboratory Practice (GLP) principles and Good Clinical Practice (GCP).

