The participant is responsible to collect tw stool samples the week after the three NB-UVB light exposures and store it in the freezer. The research coordinator will contact the participant when and where to pick up the stool samples, or participant can drop them off at their own convenience at the Skin Care Centre during on Monday, Wednesday and Friday nights.

The stool samples that are collected from the participant will be stored in the BCCHR in a -80C freezer, in a locked lab until all samples from all participants are collected. Once all stool samples are collected, they will be send off to the [name] Lab at the University of Ottawa for 16S rRNA sequencing. The results will be analysed and stored on the BCCHR password-secured computer.

6. Participant Information and Consent Process - Clinical Study [\[View Form\]](#)

6.1. Time to Participate How much time will a participant be asked to dedicate to the project beyond that needed for normal care?

The first visit to sign the consent form and do the Skin type assessment will take approximately 20 minutes. The visit for the first UVB exposure will take approx 20 minutes to review the exposure methods.
 The next two visits will take approximately 10-12 minutes each.
 The visits for the blood draws will take about 30 minutes, depending on the amount of waiting time of the Life Labs location.
 The total time the participant will spend to this study will be 2 hours minutes.

6.2. Time to Participate – Normal/Control Participants If applicable, how much time will a normal/control volunteer be asked to dedicate to the project?

Each participant will be treated similarly.

6.3. Risks/Harms Describe what is known about the risks (harms) of the proposed research.

The exposure to NB-UVB light will turn the skin slightly pink for 1-2 days. NB-UVB is ultraviolet radiation and could cause long term effects after excessive exposure, like skin ageing and skin cancer. The exposure from this study is equivalent to 5 min sun exposure during a summer’s day, per visit and is unlikely to have any long-term effects. Short-term side effects may include skin redness, skin dryness, triggering of a cold sore. All of these effects are minor and

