
6.11. Provisions for Consent What provisions are planned for participants, or those consenting on a participant's behalf, to have special assistance, if needed, during the consent process (e.g. consent forms in Braille, or in languages other than English).
	
Participants have to be able bodied to be able to participate in order to receive the UVB exposure. Subjects with no understanding of the English language will not be approached for involvement in the study unless a translator is present who can converse in the first language of the subject.
										

6.12. Restrictions on Disclosure Describe any restrictions
	
There are no restrictions on disclosure of information.
										

regarding the disclosure of information to research participants (during or at the end of the study) that the sponsor has placed on investigators, including those related to the publication of results. Also, indicate any plans for communicating study results to participants.
	

7. Number of Participants and Study Drugs - Clinical Study [View Form]
	

7.1. Multi-Centre Studies 7.1.A. Is this a multi-centre study (involves centres outside of those applied for under this Approval?)
	no

If known, please list the other sites below:
	

7.1.B. Is this study being submitted for ethical approval to any other Research Ethics Board?
	
Description: No

If yes, please provide the name of the REB(s) and if available, contact information:
	

7.2. Number of Participants 7.2.A. How many participants (including controls) will be enrolled in the entire study? (i.e. the entire study, world-wide)
	30

7.2.B. How many participants (including controls) will be enrolled at institutions covered by this Research Ethics Approval? (i.e. only at the institutions covered by this approval)
	30

7.2.C. Of these, how many are controls?
	0

7.2.D. Please enter any additional comments:
	

7.3. Drug approvals Enter the generic name of any investigational drug(s) not yet approved or any marketed drug(s) used outside of its approved indication.
	N/A

7.4. Marketed Drugs Enter the name of any marketed drug(s)
	N/A

used within its approved indication.
			

7.5. Natural Health Products Enter the name of any Natural Health Products used:
	N/A		

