8.3. Study Stoppage Describe the circumstances under which the ENTIRE study could be stopped early. Should this occur, describe what provisions would be put in place to ensure that the participants are fully informed of the reasons for stopping the study.	Circumstances under which the entire study could be stopped would be very unlikely because the study includes healthy participants and the photo therapy irradiance dosages have been established by dermatologists. In case more than 50% of the included participants will have adverse side effects (lasting burning sensation and redness of the skin) from the UVB exposure(s), the study will be stopped early. The participants will be contacted by email about the situation and will be given the option to withdraw the biological samples, in case they are already collected, the samples will be discarded in the bio hazard waste disposal.
8.4. Personal Identifiers 8.4.A. Describe how the identity of the participants will be protected both during and after the research study, including how the participants will be identified on data collection forms.	The blood and stool samples will be marked with a study identifier (A,B,C,...) in executive letters to keep track what samples belong to which participant. This identifier will also be written on a master list that will be kept separately from the other participant information. The master list will be stored on a password protected computer in the BCCHR. There wont be any other personal details written on the samples to protect the identity of the participant.
8.4.B. Will any personal health information or personal identifiers be collected?	no
If yes, please describe what personal identifying information will be collected, and justify the need for it to be collected.	N/A

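### Section 5.3 excludes only on light-related grounds, so women whose gut bacteria are shifting because of antibiotics or probiotics can enter an uncontrolled before/after comparison and add noise to it

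*Combined protocol and SAP*

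**What the plan says.** Section 5.3 (Exclusion Criteria) lists four grounds: photosensitivity, photosensitising medication, travel to a sunny place since October 2017, and regular tanning-bed use. The first two read: "The participants will be excluded if they have skin photo sensitivity or taking medication that promotes photo sensitivity of their skin". Section 5.2 (Inclusion Criteria) adds sex, ethnicity, age 19-40, Fitzpatrick type I-III and good health, which is not defined. The supplied text does not mention antibiotics or probiotics.

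The outcome is stool microbiota by 16S rRNA sequencing. Under Statistical analysis, section 5.1.B says: "The statistical analysis will focus the personal microbiota composition variation after NB-UVB light exposure in comparison to before the UVB light exposure". Section 5.5 says: "Each participant will serve as her own control". Section 7.2 gives 30 participants, and to the question "Of these, how many are controls" the answer is 0.

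On timing, section 5.7 says: "The participant is responsible to collect two stool samples during the week prior to the first light exposure". After exposure: "The participant is responsible to collect tw stool samples the week after the three NB-UVB light exposures". The three exposures fall on Monday, Wednesday and Friday of one week.

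**The concern.** The plan protects the exposure side carefully: winter timing, and exclusion of women with other recent UVB. It gives the outcome side no matching protection, although antibiotics and probiotics act on the quantity being measured.

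Three kinds of women pass section 5.3 as written: one still recovering from an antibiotic course, one who takes a course between the two stool windows, and one who starts or stops a probiotic in that time. Steady use cancels in a within-woman difference, but a change does not. With no unexposed group, nothing else in the design absorbs it.

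What is at stake is mainly precision. Unrelated changes in mixed directions widen the spread of the before/after differences, so a real UVB change is harder to see. Objective 3 asks whether a larger cohort is worthwhile, and this comparison will inform that judgement.

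**Working it through.** **1. What 5.3 covers.** All four exclusions concern light sensitivity or prior UVB. None concerns the gut.

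**2. How long a change has to occur.** The shortest span is from the Saturday before the first Monday exposure to the Sunday after the Friday exposure, which is 8 days. The longest is from Monday of the week before to Sunday of the week after, which is 20 days.

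**3. Inputs for size.** From the documents: n = 30, paired, no controls. They give no test, alpha, SD, effect size or power, so there is no planned figure to reproduce. The rest is assumed:
- two-sided 5% test
- SD of the usual before/after change in a taxon = 1
- true effect 0.53 SD, which gives 80% power with a paired t-test at n = 30
- a fraction f of women with an extra unrelated shift of k SD in random direction

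**4. Expected number affected.** 30 × 0.01 = 0.3 and 30 × 0.05 = 1.5 women. The chance of at least one is 1 − 0.99^30 = 26% and 1 − 0.95^30 = 79%.

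**5. Hand approximation.** The variance of change becomes 1 + f·k². With the normal-theory effect (1.960 + 0.842)/√30 = 0.51, power ≈ Φ(2.802/√(1 + f·k²) − 1.960).
- f = 5%, k = 1: variance 1.05, power Φ(0.774) = 78%.
- f = 5%, k = 3: variance 1.45, power Φ(0.367) = 64%.
- f = 1%, k = 3: variance 1.09, power Φ(0.723) = 77%.

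**6. Simulation** (40,000 trials per case; a repeat run agreed within about one percentage point). The number affected is binomial. Power, paired t-test / exact Wilcoxon signed-rank:

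| Affected | 1 SD | 3 SD | 5 SD |
|---|---|---|---|
| none | 80 / 78% | – | – |
| 1% | 80 / 78% | 77 / 77% | 73 / 77% |
| 5% | 78 / 77% | 66 / 70% | 52 / 68% |

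The loss is negligible for 1 SD shifts, and at 1% prevalence with a rank test. It is material when shifts are large and about 5% of women are affected.

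**7. False positives.** With no UVB effect and random directions, the error rate stays at 4-5%. If every affected woman shifts the same way (5% prevalence, 3-5 SD), it is 8-9% (t-test) or 7% (Wilcoxon). Exactly three women shifting together give 14-18% or 11%, and the chance of three or more affected at 5% prevalence is 19%.

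**8. What an entry exclusion can do.** Of the three routes, only recovery from an earlier course is already present at entry. The other two begin later. If the exclusion halved prevalence from 5% to 2.5% (an assumption), power at 3/5 SD would be about 72/63% (t-test) or 74/73% (Wilcoxon), still short of the clean 80/78%.

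**9. What a sensitivity analysis can do.** Leaving out all affected women at 5% prevalence gives about 78% (t-test) or 76% (Wilcoxon) power, with 5% false positives. This assumes that every change is reported.

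**The case against.** **The size is assumed.** No prevalence or shift size comes from the documents, and the range includes almost no effect. The lowest figure needs 5 SD shifts and a t-test, and the plan does not commit to one. This stands: the direction of the problem is certain, its size is not.

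**Partial safeguards exist.** The health requirement and the photosensitising-medication rule may remove some antibiotic users. On the first exposure day participants go to the clinic, "where the participants will be assessed under supervision of" a physician, although that assessment is described as being for the UVB exposure. Two samples per period average day-to-day variation and may reveal drift in a woman still recovering, which the one-score-per-woman calculation does not model. None of these is written for this purpose, and none reaches a change that begins after the second baseline sample.

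**Changes may already be recorded.** Paper record forms are mentioned in section 8.5.B, and a separate ethics proposal is attached under 9.1.A. Neither was supplied. A reader might infer from the negative answer to "Will any personal health information or personal identifiers be collected" that nothing is asked. That box joins health information and identifiers in one question, so it does not prove this. The gap in 5.3 stands regardless, because that box asks for the exclusion list.

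**Objective 3.** A reader might infer that lost power would wrongly end the research. No section makes a significance test decide objective 3, and the funding title in section 2.3 calls the work a pilot.

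**Conclusion.** The omission in section 5.3 is real and should be fixed. It does not invalidate the study. An uncontrolled within-woman comparison admits women whose microbiota is changing for an identifiable other reason, and the plan as supplied does not exclude them or set their changes apart.

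Confidence is high on the omission and its direction, moderate on whether such changes go unrecorded, and low on size. The power figures rest on assumed prevalence and shift size.

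Two stronger readings are not supported. The first is that an entry exclusion would restore nearly all the lost power. It cannot stop changes that start after entry, and nothing in the documents says what share arises before. The second is that the gap makes a false UVB signal likely. That needs several women shifting the same way; isolated or mixed changes leave the error rate at about 5%.

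**What to change.** 1. In section 5.3, add an exclusion for systemic antibiotic use, and for starting or stopping a probiotic, within a look-back window before the first stool sample. The investigators should choose and justify the window. This reduces contamination present at entry but not changes that start later.
2. At the existing contacts (consent meeting, the three exposure visits, stool hand-over), ask about antibiotic and probiotic changes through the last stool sample, or confirm that the record forms already do. If questions are added, check that the answer in 8.4.B still fits.
3. Keep every woman in the main analysis, so that nothing learned after exposure decides who is counted. Pre-specify a sensitivity analysis without those who report a change, and report both.

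The cost is one line in 5.3, a few questions at contacts that already take place, one extra analysis and slightly slower recruitment. The two analyses may sometimes disagree, and both results should then be shown.

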5.1. Study Summary 5.1.A
Provide a short summary of the project written in lay language suitable for non-scientific REB members. DO NOT exceed 100 words and do not cut and paste directly from the study protocol.

This research will explore the potential effects of Narrow-Band Ultra Violet B (NB-UVB) radiation on the intestinal microbiota composition and confirm a regulatory skin-to-gut axis during baseline conditions. Changes in the intestinal microbiota composition caused by NB-UVB phototherapy could be beneficial for patients with chronic/auto-inflammatory diseases like IBD by removing dangerous bacteria, increasing beneficial bacteria, and ultimately modulating immune responses.

5.1.B Summarize the research proposal: Purpose, Hypothesis, Justification, Objectives, Research Design and Statistical Analysis

Purpose:
 To explore the potential effects of Narrow-Band Ultra Violet B (NB-UVB) radiation on the intestinal microbiota composition in humans and confirm a regulatory skin-to-gut axis during baseline conditions.

Hypothesis:
 Humans exposed to UVB-NB light will show changes in the intestinal microbiota composition with selection of certain phyla of bacteria.

Justification:
 To date, there is no data that describes a biological response to UVB light in the body that affects the intestinal microbiota. Changes in the intestinal microbiota composition caused by NB-UVB phototherapy could be beneficial for patients with chronic/auto-inflammatory diseases like IBD by removing dangerous bacteria, increasing beneficial bacteria, and ultimately modulating immune responses.

Objectives:

1. Establish if there is an skin regulatory response towards NB-UVB light in humans.
2. Examine what changes in the microbiota composition can be observed on bacterial phyla and class level.
3. Determine if this research is worth pursuing in a larger cohort.

Research design:
 During the first visit, the skin type will be assessed by using the Fitzpatrick skin type questionnaire. Subsequently, subjects will be exposed three times within one week to full body NB-UVB light in The Skin Care Centre to a sub erythemic dose (cause slight redness of the skin but not burning). The exposures will happen during the winter months to prevent UVB exposure from the sun during daily activities to interfere with our observations. Stool samples will be collected before the first exposure (2x) and after the last exposure (2x) to analyse the

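### Section 5.3 excludes only regular tanning-bed users, and the form as shown neither asks women to avoid outside UVB up to the fourth stool sample nor records it

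*Combined protocol and SAP*

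**What the plan says.** The exclusion criteria (5.3) treat two sources of earlier UVB in one sentence. It opens with holidays: "Also participants that have been on vacation to a sunny destination since October 2017". It then turns to tanning beds, where the women excluded are those who "visit tanning beds on a regular basis will be excluded because they have been exposed to UVB radiation". The reason given is the same for both.

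The form has three other elements that bear on outside UVB:

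- Season (5.1.B, research design): "The exposures will happen during the winter months to prevent UVB exposure from the sun during daily activities to interfere with our observations".
- A biomarker (5.1.B): serum 25-hydroxy vitamin D is measured before and after the exposures, and is described "as a marker of previous UVB exposure before the experiment".
- A questionnaire (5.7): "the Fitzpatrick skin type will be assessed with the hand of a questionnaire about the sun exposure habits".

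For the timing of samples, 5.7 says of the baseline pair: "The participant is responsible to collect two stool samples during the week prior to the first light exposure". The second pair consists of "stool samples the week after the three NB-UVB light exposures and store it in the freezer". The analysis compares each woman after exposure with herself before it (5.1.B). Section 7.2 gives 30 participants, of whom 0 are controls.

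**The concern.** The comparison is interpretable only if the study sessions are the main UVB difference between the two pairs of samples. The holiday rule has a start date and no frequency test. The tanning rule has a frequency test, with no definition and no look-back. A woman who used a tanning bed once, shortly before her baseline samples, can therefore pass a criterion whose stated purpose is to keep out women already exposed to UVB.

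The summary of procedures in 5.7 also contains no request to avoid tanning beds or sunny travel once a woman has consented, no re-check at the exposure visits, and no place to record outside UVB. At the first exposure visit the coordinator confirms stool collection only.

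At stake is the single before/after contrast. It also feeds the third objective, whether a larger cohort is worth pursuing. A diluted change could end a useful line of work, and a spurious one could start a larger study for the wrong reason.

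**Working it through.** The plan gives no figure on this point to reproduce. It states a sample of 30 but no alpha, power, effect size or standard deviation. The check is therefore a reading of the text, a count of days, and an illustration on assumed inputs.

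**1. The safeguards side by side**

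| Source of outside UVB | Before consent | Consent to fourth stool sample |
|---|---|---|
| Everyday sun | Winter timing | Winter timing, stated for the exposures |
| Sunny travel | Excluded since October 2017 | No avoidance request or record in the form as shown |
| Tanning beds | Regular users only | No avoidance request or record in the form as shown |

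The vitamin D measurement cuts across all rows, but no cut-off, exclusion rule or adjustment is attached to it. The baseline value can point to earlier exposure. The after value cannot tell study UVB from outside UVB, since both would raise it. The sun-habits questionnaire is used to assign skin type, and no eligibility decision on outside UVB is linked to it.

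**2. Length of the open period**

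Take day 0 as the Monday of the first exposure, so the third exposure on Friday is day 4. Consent is about one week earlier (6.6), day −7. If the after week starts on the Saturday it runs from day 5 to day 11, and the span is 11 − (−7) + 1 = 19 days. If it is the following Monday to Sunday it ends on day 13, and the span is 13 − (−7) + 1 = 21 days. Either way it is about three weeks.

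**3. Direction of the effect**

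- Stable, long-past exposure is present in both pairs and largely cancels.
- UVB shortly before the baseline pair, if its effect is already present in those samples, moves them towards the exposed state and shrinks the change.
- UVB between the two pairs adds to the change and, with 0 controls, is attributed to the study light.

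**4. Illustration of size**

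Assumptions, none from the documents: paired normal approximation; two-sided alpha 0.05; 80% power at n = 30 without contamination; a fraction q of women with outside UVB equal in effect to the study UVB; standard deviation of the change unaffected by q.

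Standardised change giving 80% power: d = (1.960 + 0.842)/√30 = 0.51.

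- *Before baseline:* affected women show no further change, so the mean change is d(1 − q). Power = Φ(d(1 − q)√30 − 1.960). Sample size to restore 80% = 30/(1 − q)², rounded up.
- *Between the pairs, study light has no effect:* the mean change is dq. False-positive rate = Φ(dq√30 − 1.960) + Φ(−dq√30 − 1.960).

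| q | Power, contamination before baseline | Women needed for 80% | False-positive rate, contamination between pairs |
|---|---|---|---|
| 0 | 80% | 30 | 5% |
| 10% | 71% | 38 | 5.9% |
| 20% | 61% | 47 | 8.7% |
| 30% | 50% | 62 | 13.4% |

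Worked line for q = 20%: d√30 = 2.802. Power = Φ(2.802 × 0.8 − 1.960) = Φ(0.281) = 61%. Sample size = 30/0.64 = 46.9, so 47. False-positive rate = Φ(0.560 − 1.960) + Φ(−0.560 − 1.960) = 8.1% + 0.6% = 8.7%.

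**The case against.** The plan is not without protection. Winter timing deals with everyday sun. Although the sentence speaks of the exposures, its stated aim is to protect the observations, which include the after samples. Vitamin D is measured as a marker of earlier UVB, and sun habits are asked about. The tanning rule is in the present tense and could be read as continuing through the study, and two visits in one week might be called regular use. The within-woman design removes stable differences. This is also a 30-woman pilot. All of that stands, and it limits the point, but none of it gives a definition of regular use, an in-study check or a record.

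Four stronger readings are tempting and are not supported:

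- *That the winter design fails.* It was aimed at sun during daily life, and that protection remains whatever the tanning wording. At most, the season boundary is loose for the week of the after samples.
- *That a single outing outweighs the study exposure.* Section 6.3 says "The exposure from this study is equivalent to 5 min sun exposure during a summer’s day, per visit". With the second and third doses each 10% above the first (5.7), that makes 5 × (1 + 1.1 + 1.1) = 16 minutes, which invites comparison with, say, 20 minutes in the sun. But 6.3 is a statement about risk, not a dose-response relation for the microbiota. The study exposure is full-body, and no tanning-bed output is given. The comparison does not measure bias.
- *That participants are told nothing.* Section 5.7 is a summary. The form lists an ethics proposal, a consent form, recruitment material and a letter of initial contact that are not among the documents reviewed. Any of these could carry an avoidance instruction.
- *That bias has been shown.* The documents give no frequency of outside exposure.

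**Conclusion.** The point holds as a weakness in the eligibility wording and in the procedures as shown, not as a demonstrated bias. Followed as written, 5.3 can admit occasional or recent tanning-bed users, although its own rationale would keep them out. For about three weeks, outside UVB from tanning beds or travel is neither discouraged nor recorded in this form. With 0 controls, such exposure shortly before the first pair of samples or between the pairs cannot be separated from the study light.

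The size is unknown. The illustrated losses (power 71% to 50%, or a false-positive rate of 5.9% to 13.4%, for 10% to 30% of women affected) rest entirely on the assumed inputs and on outside UVB acting as strongly as the study UVB. Weaker or rarer exposure would matter less. The finding on in-study avoidance applies only to the text available. The change is worth making because it is cheap and the single-arm analysis cannot repair the problem afterwards.

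**What to change.** - In 5.3, exclude any tanning-bed use since October 2017, matching the holiday rule.
- In 5.7, ask participants to avoid tanning beds and sunny travel from consent until the fourth stool sample. Add one question at sample hand-over that records any such exposure and its date.
- In the statistical analysis text of 5.1.B, keep all women in the main before/after comparison, and pre-state a sensitivity analysis that omits those who report outside UVB.
- In 5.1.B, state that the winter window runs to the last stool sample, not only to the exposures.
- If the consent form or another attachment already has an avoidance instruction, bring 5.7 into line with it.

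The cost is a few sentences and one question. The downside is that a few occasional tanning-bed users become ineligible.
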